## 7. TREATMENT OF SUBJECTS

Approximately 320 eligible subjects will be randomized into 1 of 4 treatment arms:

- Nyxol + LDP
- Nyxol + LDP vehicle
- Placebo + LDP
- Placebo + LDP vehicle

Subjects will be randomized 1:1:1:1 into the above groups. Randomization will be stratified by iris color (light/dark irides). The number of subjects in each irides type should be as close as possible to 1:1, with a minimum of 40% within each stratum.

#### 7.1. Treatment Adherence

Following the completion of Visit 1 (Stage 1 Day 1), subjects will be dispensed Treatment 1 study drug for dosing at home in the evenings and a Treatment 1 subject diary to document dosing.

At the end of Visit 4 (Stage 2 Day 1), subjects will be dispensed Treatment 2 study drug for dosing at home in the mornings and a Treatment 2 subject diary to document dosing.

Subjects must bring their used and unused study medications and subject diaries with them to Visit 2 (Stage 1 Day 8), Visit 4 (Stage 2 Day 1), and Visit 5 (Stage 2 Day 8).

# All subjects must be instructed on the importance of following the once-daily dosing regimen for each Treatment 1 and Treatment 2 and maintaining their dosing diaries.

Treatment adherence will be measured by counting the used and unused vials at each study visit and by reviewing dosing in the subject diaries for both Treatments 1 and 2.

#### 7.2. Concomitant Medications

As noted in the exclusion criteria (Section 6.2), use of any topical prescription or OTC ophthalmic medications of any kind within 7 days of Screening is prohibited, with the exception of lid scrubs with OTC products (eg, OCuSOFT® lid scrub, SteriLid®, baby shampoo, etc.) and artificial tears, except the use of any OTC artificial tears (preserved or unpreserved) during Visit days or 15 min before or after instillation of Treatment 1 or Treatment 2.

Additionally, initiation of treatment with or any changes to the current dosage, drug, or regimen of any systemic adrenergic or cholinergic drugs (Appendix 3) within 7 days prior to Screening,

or during the study, is prohibited. However, a subject can be treated with a systemic adrenoceptor antagonist, for example, as long as the particular agent and its dose and regimen had been consistent for the 7 days prior to Screening, and there was no reason to believe that alteration would be necessary at some point later during the study. However, Flomax (tamsulosin) is specifically excluded

# If there is any question about whether a medication is acceptable, the Medical Monitor should be consulted before proceeding.

Use of all medications should be documented on the appropriate eCRF. Investigators are encouraged to contact the Medical Monitor for any questions regarding allowed medications. Judgment of continued study participation by the subject, and inclusion of this subject's subsequent visits in the safety and efficacy analysis, will be made by Ocuphire.

All medications that the subject has taken within 30 days prior to the Screening Visit and during the study will be recorded in the eCRF. The name of the drug, dose, route of administration, duration of treatment, and indication will be recorded for each medication. For combination products (eg, Contac®, Cosopt®) and non-combination products, the generic name is desired. The use of routine ophthalmic diagnostic pharmaceutical agents (eg, fluorescein and local anesthetic) will be allowed and should be documented. Any change in dosing parameters should also be recorded in the eCRF.

## 8. ASSESSMENT OF EFFICACY

# 8.1. Specification of the Efficacy Parameters

The primary efficacy endpoint is the percent of subjects with  $\geq 15$  letters of improvement in photopic binocular DCNVA and with < 5 letters of loss in photopic binocular BCDVA at 30 min post-LDP/vehicle comparing Nyxol + LDP to placebo + LDP vehicle at Visit 5 (Stage 2 Day 8). This comparison will be analyzed first using a hierarchical testing method.

Key secondary efficacy endpoints can be found in Section 5.1.

All of the efficacy endpoints will also be analyzed by mITT and PP Populations.

## 8.2. Assessing, Recording, and Analyzing of Efficacy Parameters

Visual acuity and PD assessments will be measured as described in Section 5.1.

The subject should be in the same room for all assessments, and every effort will be made to have the same person perform the measurements at all visits.

The timing for recording efficacy parameters may be found in Table 1 and Table 2.

# 8.2.1. Screening/Baseline Visit 1 (Stage 1 Day 1)

Individuals who are potential subjects will be identified by the study center to schedule the Screening Visit. If a subject successfully completes their Screening Assessments, then Visit 1 becomes the Baseline Visit. Note that Visit 1 (Screening/Baseline) assessments are recommended to be performed on the same day; however, in instances in which subjects are unable to complete the full day of assessments for Visit 1, subjects may be scheduled to return for the completion of Visit 1 within 1 week of Screening. If Visit 1 is split over 2 separate days, all Screening assessments up to and including randomization must occur on the first day, and then the subject should return to complete their post-randomization assessments on the second day.

Once a subject arrives at the study center, a member of the Site Staff will interview the individual as to their qualifications for participation in the study, and if the subject wishes to continue, the informed consent form (ICF) is signed, and a subject number is assigned.

The start of Screening includes an explanation of the study, a medical and ophthalmic history, demographics, HR and BP, urine pregnancy test (females of childbearing potential) and eligibility assessments.

The subject will then undergo manifest refraction and near add, and several VA measurements, including

The Screening assessment will also include an ophthalmic examination that includes assessment **biomic**, biomicroscopy, dry eye examination with tear break-up time testing and corneal fluorescein staining, IOP measurement (using a Tono-Pen or Goldmann Applanation tonometry), and direct or indirect ophthalmoscopy without dilation.

If all eligibility criteria are met, the subject will be randomized into the study.

At Visit 1 (Stage 1 Day 1), eligible subjects will be randomized, and the first dose of Treatment 1 will be administered at the study site at Time 0 min. Efficacy and safety measurements are made before dosing with Treatment 1 (Time 0 min) and at multiple post-dose timepoints from 30 min to 8 hours. If Visit 1 is split over 2 separate days, all Screening assessments up to and including randomization must occur on the first day, and then the subject should return to complete their post-randomization assessments in the following order on the second day (ie, confirm concomitant medications, subject questionnaire, in-office Treatment 1 dosing, ocular tolerability, followed by all other assessments at time points 0.5, 1, 3, 5, and 8 hours post-treatment). The following assessments are conducted during Visit 1:

Prior/Concomitant medication

Heart rate and BP

Pupil diameter (photopic and mesopic)

Distance-corrected near VA BCDVA
DCIVA ); all VA measurements will be made , except selected
measurements at 0 min ), which will
be measured binocularly followed by OD and OS measurements
Biomicroscopy
Intraocular pressure
Ophthalmoscopy
Ocular tolerability
Subject questionnaire

Adverse events

Treatment 1/Diary dispensing

## 8.2.2. Visit 2 (Stage 1 Day 8)

At Visit 2 (Stage 1 Day 8), efficacy and safety measurements will be made at 12 hours after the dose of Treatment 1 study medication (12-hour endpoint):

Heart rate and BP

Urine pregnancy test (females of childbearing potential)

Concomitant medications

Pupil diameter (photopic and mesopic)

Distance-corrected near VA BCDVA BCDVA , DCIVA ); all VA measurements will be made binocularly, except selected
measurements at 0 min which will be measured binocularly followed by OD and OS
measurements
Biomicroscopy
Intraocular pressure
Ophthalmoscopy
Ocular tolerability
Subject questionnaire
Adverse events

After completion of these assessments, the subject will take no study drug for the next 7 to 14 days (Washout Period), after which Stage 1 is complete.

# 8.2.3. Visit 3 (Stage 1 Day 10 ± 1 day) – During Washout Period

Measurements will be made on Visit 3 (Stage 1 Day  $10 \pm 1$  day) during the Washout Period to assess the absence of residual treatment effects:

Concomitant medications

Adverse events

At the conclusion of the Washout Visit measurements, Stage 1 of the study is complete.

# 8.2.4. Visit 4 (Stage 2 Day 1 [Day 15-22])

Visit 4 occurs after completion of the Washout Period. During Visit 4, efficacy and safety measurements will be made approximately 12 hours after the dose of Treatment 1 study medication and at multiple timepoints after the dose of Treatment 2 (at Time 0 min):

Urine pregnancy test (females of childbearing potential)

Concomitant medications

Ocular tolerability

Subject questionnaire

Adverse events

Treatment 2/Diary dispensing

## 8.2.5. Visit 5 (Stage 2 Day 8 [Day 22-29])

Visit 5 occurs 7 days after Visit 4. During Visit 5, efficacy and safety measurements will be made approximately 12 hours after the dose of Treatment 1 study medication and at multiple timepoints after the dose of Treatment 2 (at Time 0 min) [note 30 minute measurements are key secondary endpoints]:

Heart rate and BP

Urine pregnancy test (females of childbearing potential)

Concomitant medications

Pupil diameter (photopic and mesopic)

Distance-corrected near VA BCDVA BCDVA COLLECTION OF THE STATE OF THE

Biomicroscopy

Intraocular pressure

Ophthalmoscopy

Ocular tolerability

Subject questionnaire

Adverse events

Collection of used/unused Treatment 1 and Treatment 2 and subject diaries

#### 8.2.6. Unscheduled Visits

An unscheduled visit may be any visit to the Investigator other than the specific visits requested in the protocol as possibly required for the subject's ophthalmic condition. The Investigator will perform all procedures necessary to evaluate the subject at these visits and record any AEs in the eCRF.

As noted in Section 5.9.4, every possible effort should be made by Investigators to assure that subjects who discontinue early from the study have a telephone follow-up that includes assessments of AEs and concomitant medications.

09/29/2023 Page 44 of 76

#### 8.3. Visit Variation

Visit 3 may occur 1 to 3 days after Visit 2; Visit 4 may occur 8 to 15 days after completion of Visit 1; and Visit 5 may occur 22 to 36 days after Visit 1.

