#### 3.5. Study Population

The study population for this trial will be comprised of males and females between 40 and 64 years of age with presbyopia. A sample size of approximately 320 subjects will be randomized into 1 of

4 treatment arms, with the expectation that approximately 300 subjects will be evaluable for efficacy.

- Nyxol + LDP
- Nyxol + LDP vehicle
- Placebo (ie, Nyxol vehicle) + LDP
- Placebo + LDP vehicle

Subjects will be randomized 1:1:1:1 into the above groups.

At Visit 1 (Screening/Baseline), eligible subjects will be randomized, and the first dose of Treatment 1 will be administered (note: if Visit 1 is split into 2 separate days, then dosing occurs on the second day). Efficacy and safety measurements are made before dosing with Treatment 1 (Time 0 min) and at multiple post-dose timepoints from 30 min to 8 hours. If Visit 1 is split over 2 separate days, all Screening assessments up to and including randomization must occur on the first day, and then the subject should return to complete their post-randomization assessments in the following order on the second day (ie, confirm concomitant medications, subject questionnaire, in-office Treatment 1 dosing, ocular tolerability, followed by all other assessments at time points 0.5, 1, 3, 5, and 8 hours post-treatment). Prior to discharge following completion of Visit 1 (Stage 1 Day 1), Treatment 1 study medication for Stages 1 and 2 will be dispensed for evening dosing by the subject before bedtime, to begin the night of Stage 1 Day 2. On the evening prior to Visit 2, the subject will dose Treatment 1 study medication as close to 12 hours prior to Time 0 min for that visit.

At Visit 2 (Stage 1 Day 8), efficacy and safety measurements will be made at 12 hours after the dose of Treatment 1 study medication (12-hour endpoint). After completion of these assessments, **the subject will take no study drug for 7 to 14 days (during the Washout Period)**, after which Stage 1 is complete. Measurements will be made on Visit 3 (Stage 1 Day  $10 \pm 1$  day) during the Washout Period to assess the absence of residual treatment effects.

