Subjects will restart dosing daily with Treatment 1 in the evening immediately prior to Visit 4 (Stage 2 Day 1) as close to 12 hours prior to the scheduled time for Visit 4 for the 12-hour assessments. At this visit, after completion of the 12-hour assessments for Treatment 1, subjects will be administered their morning dose of Treatment 2 (at Time 0 min) at the study site, and efficacy and safety measurements will be made at multiple post-dose timepoints over the next 8 hours. During Stage 2, subjects will administer Treatment 1 in the evenings near bedtime and Treatment 2 in the mornings from the evening prior to Visit 4 (Stage 2 Day 1) for the next 7 days or until the evening before their scheduled Visit 5 (Stage 2 Day 8). On the evening prior to Visit 5, Treatment 1 should be administered as close to 12 hours prior to the scheduled time for Visit 5. At Visit 5, measurements will be made before dosing with Treatment 2 at Time 0 min and at multiple post-dose timepoints over 8 hours after dosing with Treatment 2.

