#### Ocuphire Pharma, Inc. OPI-NYXP-301

assessments are recommended to be performed on the same day; however, in instances in which subjects are unable to complete the full day of assessments for Visit 1, subjects may be scheduled to return for the completion of Visit 1 within 1 week of Screening. If Visit 1 is split over 2 separate days, all Screening assessments up to and including randomization must occur on the first day, and then the subject should return to complete their post-randomization assessments on the second day. \*Postrandomization assessments to be performed on the second day (ie, confirm concomitant medications, subject questionnaire, in-office Treatment 1 dosing, ocular tolerability, followed by all other assessments at time points 0.5, 1, 3, 5, and 8 hours post-treatment).

[b] Time of visits will be scheduled relative to the prior evening's dose of Treatment 1. Visit 2 will be scheduled such that the 0 hour (Time 0 min) assessments on Visit 2 will occur approximately 12 hours ( $\pm 1$  hour) after the prior evening's dose of Treatment 1. Visit 3 occurs at Stage 1 Day 10 ( $\pm 1$  day) during the Washout Period. [c] An additional  $\pm 5$  min is permitted for measurements at 0.5 and 1 hour; an additional  $\pm 10$  min is permitted at 3, 5, and 8 hours for Visits 1 and 2.

[d] Urine pregnancy test is for females of childbearing potential only.

[h] IOP performed with Tono-Pen or Goldmann applanation tonometry.

[i] Direct or indirect ophthalmoscopy performed without dilation. Use of 90 D lens (indirect) is allowed.

[j] Treatment 1: At Visit 1 (either first or second day of Visit 1, see \* above), one drop of Nyxol or placebo (ie, Nyxol vehicle) will be dosed at the study site after the completion of 0 hour (Time 0 min) ocular assessments. Subject will dose with Treatment 1 each evening near bedtime, starting the evening of Stage 1 Day 2 through the evening prior to Visit 2 (Stage 1 Day 8), except the evening before Visit 2, when Treatment 1 is dosed as close to 12 hours prior to Time 0 min for that visit. Subjects will discontinue dosing during the 7- to 14-day Washout Period.

[k] Ocular tolerability performed it will be assessed at the beginning of each specified timepoint after dosing at Visits 1 and 2.

[1] Subject guestionnaire (Appendix 5 and Appendix 6) will be completed by the subject at specified visits and timepoints.

Table 2:Schedule of Events for Stage 2

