Table 2. Schedule of Events for Stage	Visit 4[a]							Visit	5[a]					
	Stage 2 Day 1 (Day 15 to 22)						Stage 2 Day 8 (7 days after Stage 2 Day 1)							
Time (hr)[b]	12 hr post Treatment 1	0	0.5	1	3	5	8	12 hr post Treatment 1	0	0.5	1	3	5	8
Prior/Concomitant medications	Х							X						
Urine pregnancy test[c]	Х							Х						
HR/BP														Х
Biomicroscopy														Х
IOP[g]														Х
Ophthalmoscopy[h]														Х
AEs	Х													Х
Subject questionnaire[k]					Х							Х		
In-office Treatment 2: LDP or LDP vehicle[i]		Х							Х					
Ocular tolerability[j]		Х							Х					
Treatment 1: Nyxol or placebo and Subject							X							Х
diary dispensed / reviewed[1]							Λ							Λ
Treatment 2: LDP or LDP vehicle and Subject diary dispensed / collected[i]							X							Х

AE, adverse event; BCDVA, best-corrected distance visual acuity; BP, blood pressure; DCNVA, distance-corrected near visual acuity; HR, heart rate; ID, identification; IOP, intraocular pressure; LDP, Low-Dose Pilocarpine; OD, right eye; OS, left eye; PD, pupil diameter; VA, visual acuity.

[a] Time of visits will be scheduled relative to the prior evening's dose of Treatment 1. Visits 4 and 5 will be scheduled such that the 12 hour post-dose assessments on Visits 4 and 5 will occur approximately 12 hours ( $\pm$  1 hour) after the prior evening's dose of Treatment 1.

[b] An additional  $\pm 5$  min is permitted for measurements at 0.5 and 1 hour; an additional  $\pm 10$  min is permitted at 3, 5, and 8 hours for Visits 4 and 5.

[c] Urine pregnancy test is for females of childbearing potential only.

[g] IOP performed with Tono-Pen or Goldmann applanation tonometry.

[h] Direct or indirect ophthalmoscopy performed without dilation. Use of 90 D lens (indirect) is allowed.

[i] Treatment 2: One drop of LDP or LDP vehicle in each eye dosed daily in the mornings beginning on the day after Visit 4 and daily through the day prior to Visit 5. At Visits 4 and 5, subject will be dosed with Treatment 2 at the study site. Subject will bring Treatment 2 kit and diary to Visits 4 and 5 for review and accountability.

[j] Ocular tolerability performed it will be assessed at the beginning of each specified timepoint after dosing at Visits 4 and 5.

[k] Subject questionnaire (Appendix 5 and Appendix 6) will be completed by the subject at specified visits and timepoints.

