#### 5.5. Expected Duration of Subject Participation

The total length of subject participation is approximately 22 to 36 days (accommodating for weekends), with 5 clinic visits as summarized below:

- Screening/Baseline Visit 1 (Stage 1 Day 1). Note that Visit 1 (Screening/Baseline) assessments are recommended to be performed on the same day; however, in instances in which subjects are unable to complete the full day of assessments for Visit 1, subjects may be scheduled to return for the completion of Visit 1 within 1 week of Screening. If Visit 1 is split over 2 separate days, all Screening assessments up to and including randomization must occur on the first day, and then the subject should return to complete their post-randomization assessments on the second day.
- Visit 2 (Stage 1 Day 8)
- Visit 3 (Stage 1 Day  $10 \pm 1$  day) during the Washout Period of 7 to 14 days
- Visit 4 (Stage 2 Day 1 [Day 15-22])
- Visit 5 (Stage 2 Day 8 [Day 22-29])

The execution of the entire study (first subject screen through last randomized subject completed) is expected to take approximately 9 months.

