#### *Stage 1: Dosing of Treatment 1*

Individuals who are potential subjects are identified by the study center to schedule the Screening Visit. If a subject successfully completes their Screening Assessments, then Visit 1 becomes the Baseline Visit.

Once a subject arrives at the study center, a member of the Site Staff interviews the individual as to their qualifications for participation in the study, and if the subject wishes to continue, the informed consent form (ICF) is signed, and a subject number is assigned.

If all eligibility criteria are met, the subject is randomized into the study.

At Visit 1 (Stage 1 Day 1), eligible subjects were randomized, and the first dose of Treatment 1 was administered at the study site at Time 0 min (note: if Visit 1 is split into 2 separate days, then dosing occurs on the second day). Efficacy and safety measurements were made before dosing with Treatment 1 (Time 0 min) and at multiple post-dose timepoints from 30 min to 8 hours.

In Stage 1, the safety and efficacy of Nyxol as a single agent was evaluated after 1 day and 7 days of daily dosing.

Following Visit 2 (Stage 1 Day 8), subjects discontinued dosing Treatment 1 for 7 to 14 days (Washout Period). During the Washout Period, subjects returned for Visit 3 (Stage 1 Day 10  $\pm$  1 day) to assess the resolution of drug treatment effects.

During Stage 1, Treatment 1 is dosed daily in the evenings near bedtime starting with the day after completion of Visit 1, except for Visit 1 [Stage 1 Day 1], when the subject is dosed during the day at the study site, and the evening before Visit 2, when Treatment 1 is dosed as close to 12 hours prior to Time 0 min at Visit 2.

Analysis will consist of comparison across the 2 arms:

- Nyxol
- Placebo

*Stage 2: Dosing of Treatments 1 and 2*

Visit 4 (Stage 2 Day 1) is the start of Stage 2. In Stage 2, the efficacy and safety of Nyxol + LDP was evaluated following 1 day and 7 days of dosing, in which Treatment 1 (Nyxol or placebo) is dosed daily in the evenings near bedtime, except the evening before Visits 4 and 5, when Treatment 1 is dosed as close to 12 hours prior to the scheduled time for those visits. Treatment 2 (LDP or LDP vehicle) is dosed daily in the mornings. Treatment 2 will be dosed at the study site at the beginning of Visits 4 and 5 (Stage 2 Days 1 and 8, respectively).

Analysis consists of comparison across the 4 arms:

- Nyxol + LDP
- Nyxol + LDP vehicle
- Placebo + LDP
- Placebo + LDP vehicle

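### Protocol 8.3 lets Visit 4 fall on Days 9 to 16, while the schedule and washout place it on Days 15 to 22; only Days 15 and 16 satisfy both

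*Protocol*

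**What the plan says.** Section 8.3 of the protocol, which sets the permitted visit variation, says "Visit 4 may occur 8 to 15 days after completion of Visit 1". The same sentence puts Visit 3 at 1 to 3 days after Visit 2, and Visit 5 at 22 to 36 days after Visit 1.

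The schedule says otherwise. Table 2 heads the Visit 4 column "Stage 2 Day 1 (Day 15 to 22"), and Section 5.5 lists "Visit 4 (Stage 2 Day 1 [Day 15-22"]). Section 8.2.4 repeats that day range in its heading and adds that "Visit 4 occurs after completion of the Washout Period". On the washout, Section 3.5 says that after the Visit 2 assessments "the subject will take no study drug for 7 to 14 days (during the Washout Period"). Sections 5, 5.5 and 8.2.2 give the same length.

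Three dosing statements fix the drug-free interval and the day count:

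- Table 1, footnote j: home dosing of Treatment 1 runs "starting the evening of Stage 1 Day 2 through the evening prior to Visit 2 (Stage 1 Day 8").
- Protocol 3.5: "Subjects will restart dosing daily with Treatment 1 in the evening immediately prior to Visit 4 (Stage 2 Day 1").
- SAP 5.1: "Treatment 1 is dosed daily in the evenings near bedtime starting with the day after completion of Visit 1".

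Section 8.2.5 places Visit 5 seven days after Visit 4.

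**The concern.** Two operative timing rules for Visit 4 barely intersect. A site that schedules from 8.3 can bring a subject back before the washout is over, and even before or on the same day as Visit 3, which is due on Day 10 ± 1. A site that schedules from Table 2 will mostly fall outside 8.3.

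Three things are at stake:

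- **Deviation classification.** Whether a given date is a deviation depends on which section the monitor reads, and no rule of precedence appears in the visible text.
- **Stage 2 per-protocol membership.** SAP 7.1.3 excludes subjects with major deviations judged to have a significant impact on Stage 2 outcome. SAP 8.2 leaves that judgement to a blinded sponsor review before database lock, and that review needs a single window.
- **Meaning of Visit 4.** A short interval after Visit 2 could blur Visit 4 as a first-day result after washout.

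**Working it through.** **Inputs.** Visit 1 = Day 1 and Visit 2 = Day 8 (5.5). Washout = 7 to 14 days (3.5, 5, 5.5, 8.2.2). The 8.3 window for Visit 4 = 8 to 15 days from completion of Visit 1. Last Stage 1 home dose = evening of Day 7, the evening before Visit 2 (Table 1, footnote j). Restart = evening before Visit 4 (3.5). Visit 4 to Visit 5 = 7 days (8.2.5).

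**1. Reproduce the schedule.** Visit 4 = 8 + 7 to 8 + 14 = Days 15 to 22, as printed. Visit 5 = 15 + 7 to 22 + 7 = Days 22 to 29, as printed in 5.5 and 8.2.5.

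**2. Check how 8.3 counts days.** Visit 3 = 8 + 1 to 8 + 3 = Days 9 to 11, which equals Day 10 ± 1. So 8.3 counts elapsed days.

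**3. Convert the 8.3 window for Visit 4.** 1 + 8 to 1 + 15 = Days 9 to 16.

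**4. Compare.** For Visit 4 on Day d, days since Visit 2 = d − 8. Skipped evening doses are those of Days 8 to d − 2, so their number is d − 9.

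| | 8.3 | Table 2, 5.5, 8.2.4 |
|---|---|---|
| Visit 4, study day | 9 to 16 | 15 to 22 |
| Days after completion of Visit 1 | 8 to 15 | 14 to 21 |
| Days after Visit 2 | 1 to 8 | 7 to 14 |
| Evening doses skipped | 0 to 7 | 6 to 13 |
| Days outside the other window | 6 of 8 (9 to 14) | 6 of 8 (17 to 22) |

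The overlap is Days 15 and 16. On Day 9, the last dose is on the evening of Day 7 and the restart on the evening of Day 8, so there is no gap in nightly dosing.

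**5. Split Visit 1.** Footnote j starts home dosing on Stage 1 Day 2, and SAP 5.1 starts it the day after Visit 1 is completed. Stage 1 Day 1 is therefore the completion day, which is also the anchor in 8.3. The comparison stays at 8 to 15 against 14 to 21 days, with two days in common.

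**6. Visit 5 within 8.3.** The sentence counts Visit 4 from completion of Visit 1 but Visit 5 from Visit 1. If Visit 1 is completed s days after its first day (s = 0 to 7), Visit 4 by 8.3 is s + 8 to s + 15 days after the first day, and Visit 5 is s + 15 to s + 22. The number of those eight days inside 22 to 36 is s + 1:

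- s = 0: Visit 5 at 15 to 22 days, 1 of 8
- s = 3: Visit 5 at 18 to 25 days, 4 of 8
- s = 7: Visit 5 at 22 to 29 days, 8 of 8

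**The case against.** The best reply is that 8.3 is one permissive sentence set against a washout stated in several places. A site using Days 9 to 14 would breach those statements, so a visit with no washout requires following 8.3 alone. That is fair on likelihood: the figures show what the sentence permits, not what is expected to happen. It does not make the sentence consistent with the rest.

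The counts also depend partly on the reading:

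- **Inclusive counting.** If Visit 1 is day 1 of the count, 8.3 gives Days 8 to 15 and only Day 15 overlaps.
- **Washout counted strictly from Visit 2 to the restart.** A Day 15 visit restarts on the evening of Day 14, about 6.5 days after a morning Visit 2, so only Day 16 meets every statement. Counted from the last dose (evening of Day 7), the interval is 7 days and Day 15 also qualifies.
- **Days numbered from Screening, with a 7-day split.** 8.3 then gives Days 16 to 23, which largely overlaps the printed 15 to 22. But Visit 2 plus washout moves to Days 22 to 29, and again only two days (22 and 23) meet both 8.3 and the washout.
- **The Visit 5 range read as day numbers.** A same-day Visit 1 gives Visit 5 on Days 16 to 23. Two days then qualify instead of one, and the conflict ends at a 6-day split instead of 7.

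None of these readings leaves more than two days for Visit 4 once the washout is respected. The Visit 5 counts are less firm and should be taken as conditional.

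It is also true that the consequences are limited. The Stage 2 per-protocol definition has no explicit visit-window criterion, and the examples of major deviations in Section 13.3 do not mention visit timing. Exclusion would need a specific judgement of impact.

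**Conclusion.** The contradiction is in the current protocol text and holds. On the plain elapsed-day reading, which the Visit 3 clause supports, two of eight Visit 4 days agree and six of eight in each window fall outside the other. A split Visit 1 does not resolve it. The Visit 5 inconsistency inside 8.3 is secondary: it is greatest for a same-day Visit 1 and disappears at a 7-day split.

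The consequence is confined to deviation classification, possible Stage 2 per-protocol membership and the interpretation of Visit 4. The Stage 1 per-protocol population is not affected. No effect on the mITT primary analysis is shown: Treatment 1 assignment carries over from Stage 1, baseline is taken at Visit 1, and mITT membership does not depend on visit windows. The point should be corrected, but it does not threaten the primary result.

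**What to change.** Reconcile Section 8.3 with Table 2, Sections 5.5, 8.2.4 and 8.2.5, and the washout statements. Visits 4 and 5 should each have one window counted from one named anchor, and the text should say how a split Visit 1 is counted. It should also say whether the washout runs from the last dose or from Visit 2, and whether it ends at the restart of Treatment 1 or at Visit 4. Which passage is correct is for the sponsor to decide; this review does not choose between them.

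Apply the reconciled window in the deviation file and the Stage 2 per-protocol review before database lock. The cost is a protocol clarification or amendment and the same wording in the deviation review, with no added visits or procedures.
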